6.7. ADDITIONAL ANALYSIS

6.7.1. ASES Comparison

The comparison of the ASES Shoulder Score must compare all Total ASES Shoulder Scores of all follow-up visits against each other (m x n) in accordance to table 6.7.1.1 and the analysis tables listed in this chapter. This analysis is part of the final report only.

ASES Shoulder Score – Follow-up Visits to be compared														
Comparison		Follow-up Visits (n)												
		Preop	6 Weeks	6 Months	12 Months	24 Months	36 Months	48 Months	60 Months	72 Months	84 Months	96 Months	108 Months	120 Months
Follow-up Visits B (m)	Preop													
	6 Weeks	x												
	6 Months	x	x											
	12 Months	x	x	x										
	24 Months	x	x	x	x									
	36 Months	x	x	x	x	x								
	48 Months	x	x	x	x	x	x							
	60 Months	x	x	x	x	x	x	x						
	72 Months	x	x	x	x	x	x	x	x					
	84 Months	x	x	x	x	x	x	x	x	x				
	96 Months	x	x	x	x	x	x	x	x	x	x			
	108 Months	x	x	x	x	x	x	x	x	x	x	x		
	120 Months	x	x	x	x	x	x	x	x	x	x	x	x	

*All combinations marked with an "x" must be performed

Table 6.7.1.1: All Assessments – ASES Shoulder Score – Follow-up Visits to be compared

Evaluation Variable / Question	Level of Measurement	Analysis Plan
All Assessments – ASES Shoulder Score Comparison		
Use “ASES Total Score m [points]” and “ASES Total Score n [points]”:		
Based on the underlying distribution of the data in both groups and the result of the normality assessment, either the parametric paired samples t-test or the non-parametric Wilcoxon test will be used to compare “ASES Total Score m [points]” and “ASES Total Score n [points]” to evaluate the ASES score change by subject (improvement or decrease). The complete available SPSS tables content related to either the paired samples t-test or the Wilcoxon test will be included in the final report. (Variable(s): FINSCORE)		

Table 6.7.1.2: All Assessments – ASES Shoulder Score Comparison Tables List

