4.7. CONFIDENCE INTERVALS AND P-VALUES

The following acceptance / rejection criteria were used for this clinical investigation:

Parameter	Acceptance / rejection criteria
Confidence level (1- α)	0.95 (95%)
Significance level (α)	0.05 (5%)
Power (1- β)	0.80 (80%)
Beta-level (β)	0.20 (20%)
Confidence interval of mean	95%
p-value indicating significance	≤ 0.05

Table 4.7: Acceptance / Rejection Criteria

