5.4. ADHERENCE AND CIP DEVIATIONS

Any CIP deviations will be listed in the interim/annual and final reports. It is optional to describe this chapter in free text or present it in a tabulated format.

6. Analysis

The following tabulated analysis plan reflects this approach and specifies the variables characteristics (quantitative or qualitative) in detail together with the related analysis strategy. This also includes calculation and summaries based on primary elements and the required analysis.

All analyses described in this section, will be split in the two groups (Arm A; Arm B).

In addition, it will be defined in the text or directly in the tables below, if the variable must be included in an interim/annual report (IR) and/or in the final report (FR).

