6.7.4. ASES Total Score – Within subject changes by visit

The within subject score changes of the total ASES Shoulder Score from visit to visit will be analyzed to help identifying the changes on the subject level. This analysis is part of the final report.

The within subject changes by visit of the ASES Shoulder Score must compare all follow-up visits against each other (m x n) in accordance to table 6.7.4.1 and the analysis tables in this chapter.

		ASES Shoulder Score – Follow-up Visits to be compared												
		Follow-up Visits (n)												
Comparison		Preop	6 Weeks	6 Months	12 Months	24 Months	36 Months	48 Months	60 Months	72 Months	84 Months	96 Months	108 Months	120 Months
		Follow-up Visits B (m)	Preop											
6 Weeks	x													
6 Months	x		x											
12 Months	x		x	x										
24 Months	x		x	x	x									
36 Months	x		x	x	x	x								
48 Months	x		x	x	x	x	x							
60 Months	x		x	x	x	x	x	x						
72 Months	x		x	x	x	x	x	x	x					
84 Months	x		x	x	x	x	x	x	x	x				
96 Months	x		x	x	x	x	x	x	x	x	x			
108 Months	x		x	x	x	x	x	x	x	x	x	x		
120 Months	x		x	x	x	x	x	x	x	x	x	x	x	

*All combinations marked with an "x" must be performed

Table 6.7.4.1: All Assessments – ASES Shoulder Score – Follow-up Visits to be compared

Evaluation Variable / Question	Level of Measurement	Recode and Analysis Plan
All Assessments - ASES Shoulder Score Within Subject Changes		
Creation of variable “ASES Total Score change between m visit and n [points]” Difference between “ASES Total Score m [points]” with “ASES Total Score n [points]” (Variable(s): FINSCORE)	Quantitative, ratio	Calculate difference (could be negative or positive). Case summary with number and percentage of valid cases/values, missing cases/values (if any) and total cases/values. Mean, median, interquartile range, maximum, minimum, standard deviation, 95% confidence interval for mean, Shapiro-Wilk Test.

Table 6.7.4.2: All Assessments – ASES Total Score Within Subject Changes

7. Table Templates (Tables, Figures, Listings - TFL)

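### SAP 6.7.1 tests all 78 visit pairs per arm at p ≤ 0.05 without adjustment or descriptive status, so this additional, non-endpoint table is open to chance findings

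*SAP*

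**What the plan says.** SAP 6.7.1 asks for every visit to be set against every other: "The comparison of the ASES Shoulder Score must compare all Total ASES Shoulder Scores of all follow-up visits against each other (m x n"). Table 6.7.1.1 marks the full lower triangle of 13 time points (preoperative, 6 weeks, 6 and 12 months, then yearly to 120 months), with the footnote "All combinations marked with an 'x' must be performed". For each pair, "either the parametric paired samples t-test or the non-parametric Wilcoxon test will be used to compare" the two scores, "to evaluate the ASES score change by subject (improvement or decrease"). The full SPSS test output goes into the final report. The opening of SAP section 6 adds: "All analyses described in this section, will be split in the two groups (Arm A; Arm B").

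The rule for reading the results is general. SAP Table 4.7 has a row "p-value indicating significance" with the entry ≤ 0.05, and protocol section 11 applies the same threshold to all hypothesis tests. Neither document contains an adjustment, a testing order or a descriptive label for this grid.

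On missing scores, SAP 4.6 only promises counts and percentages. SAP 6.7.4 covers the same pairs a second time (it "must compare all follow-up visits against each other (m x n")), but by estimation: a case summary and the mean change with its 95% confidence interval. Section 6.7.1 stands under the additional analyses and is for the final report only.

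**The concern.** A grid of this size, read under a flat 5% rule, can be expected to produce some significant changes when nothing has changed. Follow-up runs to ten years and the study supports post-market performance, so a reader may well look here for late loss or gain of function. A chance decrease between, say, 48 and 84 months would carry the same label as a real one.

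A second difficulty lies in comparing cells. A paired test uses only subjects with both scores. Subjects leave over time, and SAP 3.1.1 repeats the ASES annually only in subjects with full or partial implant survival. Late cells therefore rest on a smaller, selected group. A contrast between an early and a late cell mixes change over time with change in who is measured.

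**Working it through.** The plan gives no count of tests and no error rate for this analysis, so there is no figure of its own to reproduce.

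**Number of tests.** 13 time points give 13 × 12 / 2 = 78 pairs per arm, and 2 × 78 = 156 in total.

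**Which nulls can be true.** Preoperative and early postoperative scores probably differ from later ones, so I do not treat all 78 nulls as true. Suppose ASES is flat from a given visit onward:

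- from 12 months: 10 visits, 10 × 9 / 2 = 45 pairs, 45 × 0.05 = 2.25 expected false positives per arm
- from 24 months: 9 visits, 36 pairs, 1.8 expected
- from 36 months: 8 visits, 28 pairs, 1.4 expected

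**Chance of at least one.** The independence formula, 1 − 0.95^45 = 90%, does not apply because pairs share visits. Two calculations allow for that, both two-sided at 0.05:

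1. *Complete data, large sample.* With equal correlation this is the probability that the studentized range exceeds 1.96 × √2. With correlation decaying over time (0.7, 0.9 or 0.99 per year) it was simulated.
2. *50 per arm with permanent loss.* Paired t-tests, 5,000 simulated trials per setting (Monte Carlo standard error about 0.7 points). Loss is at a constant rate reaching 56% at 120 months. Correlation is equal (0.5 or 0.7) or decaying (0.7 or 0.9 per year).

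| ASES flat from | True-null pairs | Complete data | 50 per arm, 56% permanent loss |
|---|---|---|---|
| 12 months | 45 | 51–63% | 57–69% |
| 24 months | 36 | 47–57% | 53–63% |
| 36 months | 28 | 42–51% | 47–56% |

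The low ends come from strongly decaying correlation and the high ends from equal correlation. If the arms are independent, the chance of at least one false finding in either arm is 1 − (1 − f)². With complete data that is 76–86%, 72–82% and 66–76% for the three rows.

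**Who is in each cell.** Under permanent loss, a pair uses the subjects still present at its later visit. The later visit can be any of 12, so the 78 tests rest on at most 12 subject sets. At a constant rate the number present at month t is 50 × 0.44^(t/120): about 46 at month 12, 42 at month 24 and 22 at month 120.

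**Assumptions not in the documents.** These are the arm split (only the total of 100 is given), the correlations, the timing of loss, and two-sided testing (6.7.1 states no sidedness but looks for change in both directions). The 56% is itself used inconsistently: the sample-size tables add 6 to 10, and 6/16 is 37.5% loss. A loss of that size should fall between the two columns. The simulation used t-tests throughout and did not model the choice between t and Wilcoxon.

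**The case against.** The strongest reply is that little hangs on this table. The endpoints are the 24-month ASES against a fixed value, device-related adverse events and implant survivorship. No success criterion uses the grid, and SAP 4.2 sets no stopping rules. That stands, and it limits the weight of the point. It does not remove it: being listed as additional does not exempt the tests from a threshold that the protocol applies to all hypothesis tests.

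A reader might infer that the grid is the plan's evidence on durability of function. The documents do not support that. SAP 6.5 gives the mean score with a 95% interval at each visit, 6.7.4 gives every pairwise change with its interval, and 6.7.3 gives time to reoperation. The grid adds mainly p-values.

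A reader might also infer that each of the 78 tests has its own set of subjects. Under permanent dropout there are at most 12 sets. Many more arise only if visits are missed intermittently (about 63 in one simulation of that pattern), and the documents do not predict this. Within any one cell the comparison remains within-subject. The mixing arises only when cells are compared with each other.

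Finally, replacing the grid outright with a linear mixed model would conflict with SAP 4.10, which calls for non-parametric methods when normality fails and rules out transformation. An unstructured covariance over 13 visits would also need 13 × 14 / 2 = 91 parameters, with perhaps 22 subjects per arm left at year 10. That objection is sound, so the model is only an option below.

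**Conclusion.** The point holds in a limited form. The SAP orders 156 tests, a general rule makes each p ≤ 0.05 significant, and nothing adjusts them or labels them descriptive. The primary error rate is not touched.

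It is tempting to say without conditions that a false finding is more likely than not. Per arm, that depends on when scores level off. It is better than even if ASES is flat from month 12, only modestly so or about even from month 24, and about even or below from month 36. Across both arms it was more likely than not in every setting tried. All these figures are conditional on true nulls and on the assumed arm size, loss and correlation. The count of tests and the missing rule for reading them depend on none of that. A SAP correction is worthwhile; the trial's main conclusion does not depend on it.

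**What to change.** In SAP 6.7.1:

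- State that the grid is exempt from the p ≤ 0.05 rule in SAP 4.7 and that no significance claims will be made from it.
- Report every pair as mean change with 95% confidence interval and the number of subjects in that cell. SAP 6.7.4 already calls for these. The minimum template in SAP 7.2 lists no interval, so say that it will be shown.
- Note beside the table that later cells contain only subjects still contributing scores.
- Limit formal tests to a few contrasts per arm named in advance, for example 24 vs 12, 60 vs 24 and 120 vs 24 months, with Holm adjustment.

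Optionally, estimate those contrasts from a repeated-measures mixed model on all available scores, naming a parsimonious covariance structure and amending SAP 4.10 to allow it.

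The cost is a short SAP amendment. No estimate is lost, since 6.7.4 keeps them all, and the protocol's list of additional analyses (11.3.4) names within-subject changes but not this test grid. The downside is fewer nominal p-values and, if the model is used, reliance on missing-at-random, covariance and normality assumptions.

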3.1. FRAMEWORK

All quantitative variables, including those based on calculations (secondary elements), will be analyzed with a case summary evaluation before the detailed characteristics and parameters can be evaluated. A case summary contains a listing of the number of valid cases/values, missing cases/values (if any) and total cases/values in the specific analysis. In general, as central position parameter for quantitative variables the mean, median and mode will be analyzed. As variation parameter the standard deviation, 95% confidence interval of the mean, interquartile range and range (based on maximum and minimum) will be calculated. All quantitative variables will be assessed for normality using the Shapiro-Wilk test. For optional visualization of quantitative variables, box-and-whisker plots will be used. Additional analyses like skewness and kurtosis measures or standard errors are also optional.

All qualitative variables, including those based on summaries (secondary elements), will be analyzed listing the proportions, frequencies, column and row totals, and missing proportion (if any).

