4.10. ASSUMPTIONS

In case of deviation from assumptions (e.g. normality), non-parametric methods will be used for analysis. No transformation of such data will be performed.

5. Population and Progress

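### SAP 6.7.1 chooses between the paired t-test and Wilcoxon from the data in both groups, not from the within-subject differences (minor; primary endpoint unaffected)

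*SAP*

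**What the plan says.** SAP 6.7.1 is an additional analysis for the final report. Table 6.7.1.1 marks every pair among 13 visits, from preoperative to 120 months, and requires all marked pairs to be run. The opening of SAP section 6 splits all analyses by arm. For each pair, Table 6.7.1.2 names the visit m score and the visit n score and says that "either the parametric paired samples t-test or the non-parametric Wilcoxon test will be used to compare" them. The choice is made "Based on the underlying distribution of the data in both groups and the result of the normality assessment".

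Three other places bear on this:

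- SAP 3.1: "All quantitative variables will be assessed for normality using the Shapiro-Wilk test". This includes calculated variables.
- SAP 4.10: "In case of deviation from assumptions (e.g. normality), non-parametric methods will be used for analysis".
- SAP 6.7.4, Table 6.7.4.2: each visit-to-visit difference is created and described with its mean, SD, 95% confidence interval for the mean and a Shapiro-Wilk test. Nothing links that result to the choice of test in 6.7.1.

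**The concern.** A paired t-test is a one-sample t-test on the within-subject differences. It assumes nothing about the shape of the scores at either visit. Skewed scores at both visits can give near-normal differences, and near-normal scores can give skewed ones. A rule that looks at the two visits therefore checks the wrong quantity, and it does not carry out the SAP's own principle in 4.10, which is to switch when the assumption of the test fails.

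At stake is which test and which p-value the final report shows for a visit-to-visit comparison. The report could also print a Wilcoxon result next to a Table 6.7.4.2 normality result that supports the t-test, with nothing to explain the mismatch.

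**Working it through.** **Number of comparisons.** The SAP prints no total. From the grid: 1 + 2 + … + 12 = 13 × 12 / 2 = 78 per arm, and 2 × 78 = 156 for both arms.

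**Inputs from the documents.** Benchmark mean and SD: 58.74 and 20.33 (Arm A), 74.48 and 11.08 (Arm B), SAP 3.2. Drop-out 56%, so 0.44 × 100 = 44 pairs, or 0.44 × 50 = 22 if the arms are of equal size. The split is not stated, so 10, 22 and 44 pairs were tried.

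**Assumptions not in the documents.** Shapiro-Wilk cut-off 0.05; correlation between visits 0.3, 0.6 or 0.8; normal or beta-shaped scores on 0–100; a preoperative mean and SD of 35 and 18 in one scenario; a ceiling scenario with mean 85 and SD 14.

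**Rules compared.**

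- Rule 1 (SAP, read as the two visits): t-test if Shapiro-Wilk p > 0.05 at both visits, otherwise Wilcoxon.
- Rule 2: t-test if Shapiro-Wilk p > 0.05 for the paired difference, otherwise Wilcoxon.

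**Rough check by hand.** Suppose everything is normal and the three Shapiro-Wilk tests are treated as independent. At least one visit fails with probability 1 − 0.95² = 0.0975. The rules then differ with probability 0.0975 × 0.95 + 0.9025 × 0.05 = 0.0926 + 0.0451 = 0.138, or 0.138 × 78 = 10.8 comparisons per arm. Under normality, then, the disagreement is only the false alarms of the pretest.

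**Simulation** (2,000 runs per setting). A repeat gave 13–45% for beta scores at benchmark values and 44–79% at the ceiling; the ranges below span both.

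| Assumed scores | Rules pick different tests | Of 78 |
|---|---|---|
| Normal | 12–16% | about 9.5–12 |
| Beta, benchmark mean and SD | 12–45% | about 10–35 |
| Beta, assumed ceiling | 44–80% | about 34–62 |

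**Direction.** In 8–79% of comparisons a visit fails Shapiro-Wilk while the difference passes, so Wilcoxon is used where the t-test would do. The reverse, a t-test used although the difference fails, occurs in 0–5.5%, about the false-positive rate of Shapiro-Wilk.

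**Effect on results** (beta scores, correlation 0.6, 3,000 runs each).

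- No true change, 10–44 pairs: rejection rate 0.044–0.053 under rule 1 and 0.045–0.055 under rule 2.
- True change from mean 80 (SD 14) to 86 (SD 13): power, rule 1 against rule 2, is 0.31 and 0.30 (10 pairs), 0.62 and 0.61 (22 pairs), 0.91 and 0.89 (44 pairs).
- The significance conclusion differs in 0.3–4.9% of comparisons: 0.003 × 78 = 0.2 to 0.049 × 78 = 3.8 per arm. The repeat gave about 0–5%.

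**The case against.** **The wording is loose rather than definitely wrong.** The opening of section 6 uses groups for Arm A and Arm B, and the sentence also mentions the normality assessment, which under 3.1 covers calculated variables. This stands in part. Because the row names the two visit scores, the visits are the natural reading. The arm reading does not rescue the rule: it still never mentions the differences, and it would let one arm's data decide the other arm's test although the analyses are split by arm.

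**A different test is not a wrong test.** This stands. Nearly all disagreements choose a Wilcoxon test that remains valid, and error rate and power are almost unchanged.

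**The parametric result is reported anyway.** This also stands. The 95% confidence interval for each mean difference in Table 6.7.4.2 gives the same decision as a two-sided paired t-test at 0.05. The information is not lost, although 6.7.1 may still headline the other test.

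**Stronger readings.** A reader might infer that the wrong test will be used in many of the 78 comparisons, or that the p-value of every comparison changes. The documents support neither. They give no score shape, correlation or number of pairs, so the frequency is conditional on assumptions; distributions can be constructed in which the two rules differ in most samples, but nothing in the plan points to them. Where the rules agree, test and p-value are the same.

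**Conclusion.** The rule in SAP 6.7.1 rests on the wrong quantity, and no other section repairs it. It governs 78 comparisons per arm. The share in which it would change the selected test runs from about 12% to about 80%, depending on the assumed score shape, correlation and number of pairs. In the scenarios where effects on results were simulated, the practical consequence is small: about 0–5% of significance conclusions change, and power moves by at most about 2 percentage points. The ASES visit comparisons are additional analyses; the 24-month primary test in SAP 6.6 does not depend on this rule. The point is minor, but worth correcting because a prespecified rule should be right and readable in only one way.

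**What to change.** In Table 6.7.1.2, replace "Based on the underlying distribution of the data in both groups and the result of the normality assessment" with: *Depending on the distribution of the within-subject differences (Shapiro-Wilk result from Table 6.7.4.2)*. It would help to state the Shapiro-Wilk cut-off in the same sentence. Naming one test in advance would also remove the problem, and would avoid a data-driven choice altogether.

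The cost is one sentence in the SAP. The normality test on the differences is already planned, so no new data, analyses or subjects are needed.

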6.7.2. Mortality

For analysis of the time to death or mortality, the Kaplan-Meier method will be used. The times between surgery and the most recent or last available assessment per subject will be used together with the times between surgery and the date of death. This analysis is part of the final report.

Evaluation Variable / Question	Level of Measurement	Recode and Analysis Plan
All Assessments - Mortality		
Creation of variable Difference between Date of Surgery [dd.mm.yyyy] and Date of Death [dd.mm.yyyy] in days  (Variable(s): VISITDT; DOSEDD)	Quantitative, ratio	Case summary with number and percentage of valid cases/values, missing cases/values (if any) and total cases/values. Mean, median, interquartile range, maximum, minimum, standard deviation, 95% confidence interval for mean, Shapiro-Wilk Test.
Creation of variable Difference between Date of Surgery [dd.mm.yyyy]	Quantitative, ratio	N/A (Analyzed above), used for survivorship

and Date of “most recent” Visit [dd.mm.yyyy] in days (Variable(s): VISITDT)		
Create new variable “Grouping variable - Mortality” (Variable(s): PRIMRSN)	Qualitative, nominal	- censored = survivors - events = death
Create new variable “Combined Time - Mortality” (Variable(s): VISITDT; DOSEDD)	Quantitative, ratio	- Use time between surgery and most recent visit for surviving subjects - Use time between surgery and death for deceased subject
Use variables “Combined Time - Mortality” and “Grouping variable - Mortality”	Qualitative, nominal Quantitative, ratio	Case summary with number and percentage of valid cases/values, missing cases/values (if any) and total cases/values. Kaplan-Meier survival analysis: subject ID, time, status, cumulative proportion, Kaplan-Meier estimate, standard error of KM estimate, number of cumulative events, number of remaining cases, mean for survival time with 95% confidence interval, survival graph, hazard graph.

Table 6.7.2.: All Assessments – Mortality Tables List

